#### 16.325 Adverse Event Rates

All patients who have initiated treatment will be considered evaluable for adverse event analyses. Adverse events will be summarized by frequency and severity using CTCAE v 5.0. They will be reviewed to determine overall adverse event patterns, and will be closely monitored throughout the study.

### 16.33 Correlative Research

#### 16.331 Plasma Biomarkers

In the assessment of plasma pharmacodynamic biomarkers of response

and resistance to therapy, descriptive statistics (e.g. means, standard deviations, 95% confidence intervals for continuous variables and frequencies for discrete data) and graphical analyses will be used for all correlative laboratory procedures. The associations between laboratory parameters and clinical response will be evaluated using the two-sample t-test or Fisher's exact test, as appropriate. Response rate with the corresponding 95% exact binomial confidence interval will be provided.

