Serial blood samples will be collected throughout the study according to the test table to analyze dynamic changes in cfDNA as a function of treatment. The objective is to explore the potential mutational patterns that could be associated with tumor response and disease progression. Samples will be collected from all patients. Any detected single nucleotide variants, insertions and deletions of any length, chimeric gene fusions that arise through chromosomal rearrangement, and copy number gain or copy number loss will be recorded longitudinally for each patient.

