#### 2.3 Correlative Research

2.31 To assess plasma pharmacodynamic biomarkers of response and resistance to

therapy.

2.32 To explore any correlation between tissue and blood based biomarkers and clinical outcomes.

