## 11.4 Measurement of Effect

### 11.41 Target Lesions & Target Lymph Nodes

- Measurable lesions (as defined in Section 11.21) up to a maximum of 5 lesions, representative of all involved organs, should be identified as “Target Lesions” and recorded and measured at baseline. These lesions can be non-nodal or nodal (as defined in 11.21), where no more than 2 lesions are from the same organ and no more than 2 malignant nodal lesions are selected.

**Note:** If fewer than 5 target lesions and target lymph nodes are identified (as there often will be), there is no reason to perform additional studies beyond those specified in the protocol to discover new lesions.

- Target lesions and target lymph nodes should be selected on the basis of their size, be representative of all involved sites of disease, but in addition should be those that lend themselves to reproducible repeated measurements. It may be the case that, on occasion, the largest lesion (or malignant lymph node) does not lend itself to reproducible measurements in which circumstance the next largest lesion (or malignant lymph node) which can be measured reproducibly should be selected.
- Baseline Sum of Dimensions (BSD): A sum of the longest diameter for all target lesions plus the sum of the short axis of all the target lymph nodes will be calculated and reported as the baseline sum of dimensions (BSD). The BSD will be used as reference to further characterize any objective tumor response in the measurable dimension of the disease.
- Post-Baseline Sum of the Dimensions (PBSD): A sum of the longest diameter for all target lesions plus the sum of the short axis of all the target lymph nodes will be calculated and reported as the post-baseline sum of dimensions (PBSD). If the radiologist is able to provide an actual measure for the target lesion (or target lymph node), that should be recorded, even if it is below 0.5 cm. If the target lesion (or target lymph node) is believed to be present and is faintly seen but too small to measure, a default value of 0.5 cm should be

assigned. If it is the opinion of the radiologist that the target lesion or target lymph node has likely disappeared, the measurement should be recorded as 0 cm.

- The minimum sum of the dimensions (MSD) is the minimum of the BSD and the PBSD.

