#### 16.11 Primary Endpoint

The primary endpoint for this study is overall response rate (ORR) at 36 weeks after registration, which is defined as the percentage of patients, among evaluable patients, who experience an objective response within 36 weeks. Objective response is defined as a complete or partial response per RECIST 1.1, without the confirmation scan. The evaluable patients are those who are eligible, consented, received any protocol treatment, and are not major violations.

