##### 16.211 STAGE 1:

Enter 12 evaluable patients into the study. If 0 successes are observed in the first 12 evaluable patients, we will consider this treatment ineffective in this patient population and terminate this study. Otherwise, if at least 1 success is observed, we will proceed to Stage 2.

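### Section 16.331 tests biomarkers only against responder yes/no, although the goals name clinical outcomes and progression and the trial also collects tumour-size change and PFS

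*Combined protocol and SAP*

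**What the plan says.** The goals are wider than response. Goal 2.31 reads "To assess plasma pharmacodynamic biomarkers of response and resistance to" therapy, and goal 2.32 reads "To explore any correlation between tissue and blood based biomarkers and clinical outcomes". Section 1.81 says of the serial cfDNA samples: "The objective is to explore the potential mutational patterns that could be associated with tumor response and disease progression".

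Section 16.331 is the only analysis section for these goals. Its one inferential sentence is "The associations between laboratory parameters and clinical response will be evaluated using the two-sample t-test or Fisher's exact test, as appropriate". The rest is descriptive: summary statistics "and graphical analyses will be used for all correlative laboratory procedures". A two-sample t-test needs two outcome groups, and Section 16.11 supplies the natural pair: "Objective response is defined as a complete or partial response per RECIST 1.1, without the confirmation scan".

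Other outcome data are collected. Section 3.16 requires measurable disease. Section 11.41 defines the baseline and post-baseline sums of dimensions (BSD and PBSD) and adds: "The BSD will be used as reference to further characterize any objective tumor response in the measurable dimension of the disease". Section 11.431 requires target lesions to be re-measured at each evaluation, which Section 11.1 sets at every 9 weeks. PFS and OS (Sections 16.322 and 16.323) are Kaplan-Meier summaries with no marker term. No alpha, effect size or power is given for the biomarker tests.

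**The concern.** Partial response is a 30% cut on a continuous quantity, the change from BSD. The cut is needed for the primary endpoint, but nothing in the documents requires it for the correlative work. With a yes/no outcome, a patient just short of partial response and a patient who progresses at once count the same. The test therefore says little about resistance, and the progression part of the objectives has no association analysis at all.

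The split is also very uneven. At the target ORR of 20%, 21 patients give about 4 responders (21 × 0.20 = 4.2). Near the null rate there may be none, and then the planned tests have no second group. Section 16.211 makes that a foreseeable outcome: "If 0 successes are observed in the first 12 evaluable patients, we will consider this treatment ineffective in this patient population and terminate this study". Blood and archival tissue are mandatory, so the stake is how much is learned from material every patient is asked to give. The ORR decision is not at stake.

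**Working it through.** **Inputs from the documents.** 12 patients in stage 1 and 21 in total (Section 16.21); ORR 5% under the null and 20% under the alternative (Section 16.24); first rescan at 9 weeks (Section 11.1); evaluability needs treatment but no post-baseline scan (Section 16.11); accrual is not paused between stages (Section 16.214).

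**Assumptions, because the documents are silent.** Two-sided alpha 0.05; a normally distributed marker; correlation rho between marker and tumour shrinkage, shown over a range.

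**Step 1: the plan's own figure.** The chance of no responder among 12 is (1 − p)^12: 0.95^12 = 0.54, 0.90^12 = 0.28, 0.85^12 = 0.14, 0.80^12 = 0.07. These match the stage 1 stopping row in Section 16.25, Operating Characteristics.

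**Step 2: no responder among all 21.** (1 − p)^21: 0.95^21 = 0.341, 0.90^21 = 0.109, 0.80^21 = 0.009. With no responder in the analysed set, neither planned test can be computed.

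**Step 3: power for a continuous marker, everyone scanned.** Model: x standard normal, shrinkage y = rho·x + √(1 − rho²)·e, response if y exceeds its (1 − ORR) quantile. Each scenario has 60,000 simulated trials of 21 patients. The planned analysis is the pooled t-test by responder status; a trial with no responder counts as no rejection. The alternative is Spearman on y.

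| rho | t-test, ORR 20% | t-test, ORR 10% | t-test, ORR 5% | Spearman | Gap at ORR 20% |
|---|---|---|---|---|---|
| 0.3 | 15% | 11% | 7% | 24% | 9 points |
| 0.4 | 23% | 16% | 11% | 40% | 17 points |
| 0.5 | 34% | 23% | 15% | 60% | 25 points |
| 0.6 | 49% | 33% | 21% | 79% | 30 points |

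Repeated runs agree to within about 2 points. At rho = 0 and ORR 20% the rejection rates are 0.049 (t-test) and 0.052 (Spearman), so the gap does not come from inflated error. Spearman does not depend on ORR, so the gap widens as ORR falls.

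**Step 4: patients without a post-baseline scan.** Suppose 15% are unscanned.

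- If they are exactly the patients with the worst true change, giving them the worst rank alters Spearman power by at most about 0.6 points.
- If they are unscanned for unrelated reasons, are still ranked worst, and count as non-responders in the t-test, power at ORR 20% and rho 0.4, 0.5, 0.6 is 23.2%, 34.5%, 47.7% for Spearman against 19.4%, 28.3%, 40.3% for the t-test. The gains are 3.8, 6.2 and 7.4 points.
- If the unscanned are treated as missing (17 of 21 analysed, Pearson test), power is 37%, 56% and 76%, against 23%, 35% and 48% for the t-test on all 21.

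How unscanned patients are handled therefore decides most of the gain.

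**Step 5: a discrete marker split 10/11.** With 3 responders, all in the group of 10, the two-sided Fisher p is C(10,3)/C(21,3) = 120/1330 = 0.09. With 4 it is 210/5985 = 0.035. So 3 responses, enough in Section 16.212 for a positive trial, cannot reach 0.05 at this split. A less even split can: with 5/16 it is C(5,3)/C(21,3) = 10/1330 = 0.008.

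**Step 6: PFS.** For a marker in SD units, Cox power is about Φ(√events × ln HR − 1.96). With an assumed 18 events (√18 = 4.243), HR 1.5, 1.7 and 2.0 per SD give Φ(−0.24) = 0.41, Φ(0.29) = 0.62 and Φ(0.98) = 0.84.

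**The case against.** The strongest reply is that this is open-ended exploratory work. Section 14.4 stores samples, says the laboratory may analyse them, and leaves marker selection to the time of analysis. No trial decision depends on it, and a simple group comparison is conventional. That stands as a limit on weight, but it does not explain why outcomes named in the objectives have no planned analysis.

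Four stronger readings are tempting, and the documents do not support them.

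- *The plan loses a fixed 15 to 31 points of power.* That range is one slice: Spearman, ORR 20%, rho about 0.4 to 0.6. The documents give neither rho nor alpha. At rho 0.3 the gap is 9 points, and Step 4 shows it can nearly close.
- *Tumour-size change exists for every patient and is thrown away.* Evaluability does not require a rescan, so early dropouts have no post-baseline sum. Section 16.331 also keeps descriptive and graphical analyses. The accurate statement is that these data enter no planned association test.
- *A 0/12 stop leaves no responder.* Accrual continues between stages. At 1 patient a month (Section 16.23), about 8 more could enrol while the twelfth completes 36 weeks. The chance of no responder among 20 is 0.95^20 = 36%, 0.90^20 = 12% and 0.80^20 = 1%.
- *Worst-ranking everyone unscanned is harmless.* It is harmless only if the unscanned truly did worst.

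It is also fair to say that baseline-marker analyses alone would not address acquired resistance. More tests across a panel of over 15 proteins (Section 14.412) also add false positives. The fix has to deal with both.

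**Conclusion.** The point holds as a planning gap in an exploratory analysis. Goal 2.32 and Section 1.81 name clinical outcomes and progression, Section 16.331 tests response alone, and the outcome data that would fill the gap are already collected. This rests on the text and needs no simulation.

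The size is conditional. Under the Step 3 assumptions, with every patient scanned and ORR 20%, using best percent change would raise power by about 9 points at rho 0.3 and by 17 to 30 points at rho 0.4 to 0.6, and by more at lower ORR. If 15% are unscanned for unrelated reasons and ranked worst, the gain at rho 0.4 to 0.6 is only about 4 to 7 points. The model treats response as an exact cut of the analysed variable and covers continuous markers; no power comparison was made for discrete ones.

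The chance that the planned tests cannot be computed is 34%, 11% and 0.9% for 21 patients at ORR 5%, 10% and 20%. Among the 12 stage 1 patients it is 54%, 28% and 7%, although later-enrolled patients may still respond. The problem is real near the null and minor at the target rate. The primary ORR conclusion is unaffected. The change is worth making because it is cheap.

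**What to change.** Amend Section 16.331, labelled exploratory, before outcome data are examined:

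1. For continuous baseline markers, use the Spearman correlation with best percent change from BSD. For discrete markers, compare best percent change between marker groups with a Wilcoxon rank-sum test. Give the worst rank only to patients with early progression or death before a scan. Treat patients unscanned for other reasons as missing, with worst rank as a sensitivity analysis.
2. Fit a univariable Cox model of PFS on the baseline marker.
3. For on-treatment markers, such as the change at Cycle 2 Day 1, run the same analyses from a landmark at that visit.
4. Keep the responder versus non-responder comparison as descriptive support.

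The cost is SAP wording and a few lines of code, with no new data, visits or patients. There are two downsides. A few more exploratory tests are reported without multiplicity adjustment, which the text should say. Best percent change also ignores new and non-target lesions, which is why the PFS analysis sits beside it.

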#### 16.4 Data & Safety Monitoring

##### 16.41 Review

The study chair(s) and study statisticians will review the study at least twice per year to identify accrual, adverse event, and any endpoint problems that might be developing. The Mayo Clinic Cancer Center (MCCC) Data Safety Monitoring Board (DSMB) is responsible for reviewing accrual and safety data for this trial at least twice per year, based on reports provided by the study statistician. Any safety issues requiring protocol changes are communicated through protocol amendments.

##### 16.42 Adverse Event Stopping Rules

The monitoring rule specified below is based on the knowledge available at study development. We note that the Adverse Event Monitoring Rule may be adjusted in the event of either (1) the study re-opening to accrual after any temporary suspension or (2) at any time during the conduct of the trial and in consideration of newly acquired information regarding the adverse event profile of the treatment(s) under investigation. The study team may also choose to suspend accrual because of unexpected adverse event profiles that have not crossed the specified rule below.

Accrual may be temporarily suspended to this study if at any time we observe events considered at least probably related to study treatment (i.e., an adverse event with attribute specified as "probable" or "definite") that satisfy any of the following:

- If 3 or more patients in the first 9 treated patients (or 35% or more of all patients after 9 are treated) experience a grade 4 or 5 adverse event at least probably related to treatment.

We note that we will review all Grade 4 and 5 adverse events to verify their attribution and to monitor the emergence of a previously unrecognized treatment-related adverse event.

### 17.0 Pathology Considerations/Tissue Biospecimens

#### 17.1 Tissue Biospecimen Submission

##### 17.11 Summary Table of Tissue Biospecimens for This Protocol

Type of tissue biospecimen to submit	Mandatory or optional	When to submit	Reason for submission (background/methodology section)	Where to find specific details for biospecimen submission
FFPE tissue block with corresponding H&E slide or up to twenty-five (25) 4-micron, unstained slides and up to three (3) corresponding H&E slides from primary tumors present prior to study entry (if primary tissue not available, please use tissue from metastatic lesions)	Mandatory	Within 90 days from randomization	Correlative studies (Section 17.3)	Section 17.2

## 17.2 Paraffin Embedded Tissue Blocks/Slides

17.21 Submit one formalin fixed paraffin-embedded (FFPE) tumor tissue block with largest amount of invasive tumor (at least 1 cm of tumor for cases of surgical resection) from original surgery at the time of diagnosis. Biopsy material obtained at the time of metastatic diagnosis may be submitted, if blocks from the surgical resection are inadequate or unavailable **a corresponding H&E slide for each submitted block must be provided**. The H&E slide for each block should be reviewed by the institution's pathologist to assess tissue quality prior to submission.

17.22 The FFPE tissue block is preferred; however, **if an institution is unable to provide a tissue block**, cut up to 25 (twenty-five) 4-micron sections and mount on charged glass slides. **Label the slides with ACCRU patient ID number, accession number, and order of sections, and thickness of sections.** NOTE: do not place "sticky" labels directly on slides, the institution label needs to be visible.. H&E stain every tenth slide (i.e., slides labeled 1, 11, 21, etc.). The H&E slides should be reviewed by the institution's pathologist to assess tissue quality prior to submission. For samples containing less than 7 square millimeters of tumor tissue, multiple sections should be mounted onto each slide to ensure that the appropriate amount of tumor tissue is available. Ideally, each slide should have a minimum of 75% tumor tissue on the slide to be deemed adequate for study. **Do not bake or place covers slips on the slides.**

17.23 The following materials below are mandatory (unless indicated otherwise) and required for shipment:

- Paraffin embedded tissue blocks with corresponding H&E slide(s) (OR up to 25 (twenty-five) unstained slides with corresponding H&E slide(s)).
- Specimen Submission: Tissue form
- Surgical Pathology Report
- Operative Report (*optional*)

NOTE: Please include the ACCRU patient ID number on all materials listed above.

- 17.24 The block/slides must be appropriately packed to prevent damage (e.g., slides should be placed in appropriate slide container) and placed in an individual plastic bag. Label the bag with the protocol number, ACCRU patient ID number, and patient initials.
- 17.25 Tissue specimens must be shipped  $\leq$ 90 days from date of registration.
- 17.26 Verify that the appropriate sections of the Specimen Submission: Tissue form are completed and filled in correctly. Enter information from the Specimen Submission: Tissue form into the remote data entry system on the same day the specimen is submitted (see Forms Packet).
- 17.27 Ship all block/slide tissue specimens and accompanying materials to the ACCRU Research Base:

- 17.28 When an appropriate request is submitted, the ACCRU Operations Office will forward the block(s) to the [REDACTED] At study completion specimens will be sent to the Duke Phase I Biomarker Laboratory located at Duke University for processing as outlined in Section 17.3.

### 17.3 Study Methodology and Storage Information

Submitted tissue samples will be analyzed as follows:

- 17.31 At the completion of the study, any unused/remaining material will be stored in Duke Phase I Biomarker Laboratory located at Duke University for future research according to the patient consent permission (see Section 6.5). Potential future research may include immunohistochemistry (IHC) analyses to analyze predictive biomarkers, changes in expression pattern with therapy, and correlation with response and/or adverse events. When a protocol is developed, it will be presented for IRB review and approval.

17.32 Banking of tumor tissue, according to the patient consent permission (see Section 6. 5), is for future research. As protocols are developed, they will be presented for ACCRU and IRB review and approval. (This collection is part of a general strategy of investigation for ACCRU studies).

17.33 The institutional pathologist will be notified by the Pathology Coordinator if the block may be depleted.

17.34 Blocks requested to accommodate individual patient management will be returned promptly upon request.

17.35 Return of Genetic Testing Research Results: No genetic specimens will be collected from tissue biospecimens for this study. If future genetic testing is being requested for stored tissue, patient reconsent is required.

## 18.0 Records and Data Collection Procedures

All data must be entered by Remote Date Entry (RDE) and completed by qualified and authorized personnel. Access the RAVE RDE system through the iMedidata portal at [REDACTED]. All data on the CRF must reflect the corresponding source document. Please refer to the ACCRU website for instructions ([REDACTED]).

### 18.1 Submission Timetable

#### Initial Material(s)

CRF	Active-Monitoring Phase (Compliance with Test Schedule Section 4.0)
Institutional Contacts	
On-Study	
On-Study: Prior Surgery 	
On-Study: Prior Systemic Therapy	
On-Study: Prior Radiation 	
Adverse Event: Baseline	
RECIST Measurements: Baseline	
Laboratory Tests & Results: Baseline	
Supporting Documentation: Baseline 	≤2 weeks after registration
Specimen Submission: Blood (Baseline) (see Section 14.0)	
Specimen Submission: Tissue (Baseline) (see Section 17.0)	
Patient Status: Baseline	
Notice of New Primary 	
OP and Path Reports (see Section 17.0) 	
Imaging Report 	
Patient Questionnaire Booklet-PRO/QOL: Linear Analogue Self Assessment (LASA)	≤ 2 weeks after registration - Patient questionnaire booklet must be used; copies are not acceptable for this submission.
PRO/QOL : Booklet Compliance	≤ 2 weeks after registration - This form must be completed

CRF	Active-Monitoring Phase (Compliance with Test Schedule Section 4.0)
	only if the (LASA) contains absolutely NO patient provided assessment information.
Off Treatment	Submit ≤2 weeks after registration if withdrawal/refusal occurs prior to beginning protocol therapy
ACCRU Deviation Form 	Submit only if applicable during all phases of the study (initial, active and observation)

1. Submit only if applicable.
2. Upload via the Supporting Documentation: Baseline form. This is in addition to the pathology material requirements for tissue submission (Section 17.0). Required items to be uploaded include: COLOMATE Companion Trial Recommendation Form (Only required if participating on ACCRU-GI-1611), Imaging Report, and Pathology report.

#### Test Schedule Material(s)

CRF	Active-Monitoring Phase (Compliance with Test Schedule Section 4.0)	
	At each evaluation during treatment	At end of treatment
Treatment (Intervention)	X	X
Treatment (Intervention): Dose Modifications, Omissions and Delays 	X	
Adverse Events: Solicited	X	X
Adverse Events: Other 	X	X
RECIST Measurements 	X	X
Supporting Documentation 	X	X
Laboratory Tests and Results	X	X
Specimen Submission: Blood (see Section 14.0) 	X	
Patient Status: Treatment (Intervention)	X	X
PRO/QOL: Booklet Compliance	X	X
Patient Questionnaire Booklet-PRO/QOL: Linear Analogue	X	X
Self Assessment (LASA) (if applicable) 		
Patient Medication Diary 	X	
PRO/QOL : Booklet Compliance (if applicable) 	X	X

CRF	Active-Monitoring Phase (Compliance with Test Schedule Section 4.0)	
	At each evaluation during treatment	At end of treatment
Notice of New Primary 	X	X
Consent Withdrawal (choose appropriate form) 		
• Consent Withdrawal: Specimen Only	X	X
•		
• Consent Withdrawal: All Follow-Up		
Off Treatment		X
ACCRU Deviation Form 	X	X

1. Submit only if applicable.
2. Upload imaging for all scans to support RECIST measurements and clinic note in the Supporting Documentation Form.
3. Patient questionnaire booklet must be used; copies are not acceptable for this submission.
4. This form must be completed only if the Linear Analogue Self Assessment (LASA) contains absolutely NO patient provided assessment information.
5. This form is to be completed by the patient and uploaded to RAVE in the Treatment (Intervention) folder for each cycle.

